1.0 Objectives

1.1 Describe the purpose, specific aims, or objectives of this research.

Response:

Aim 2 from NIH Grant: Use a Hybrid Type 1 design to simultaneously measure program effectiveness and implementation at sites randomized to implement a Mobile Markey for 1 year versus a planning condition

2a. Measure MM effectiveness at improving the following outcomes between baseline and 1-year follow-up:

- 1.) self-reported diet measured via two 24-hour dietary recalls
- 2.) BMI based on in-person height and weight measurements
- 3.) an objective indicator of fruit and vegetable (F&V) consumption (dermal carotenoids measured via finger scan)
- 4.) Social Cognitive Theory diet-related constructs including self-efficacy and food environment.

Sub-study (Funded by UB) Aim

The goal of this research is to understand:

1. Why do residents of underserved communities choose not to participate in food access programs
2. What can food access programs do improve their reach to the most vulnerable members of the community

1.2 State the hypotheses to be tested, if applicable.

NOTE: A hypothesis is a specific, testable prediction about what you expect to happen in your study that corresponds with your above listed objectives.

Response:

We hypothesize that by making F&V available in underserved communities and increasing nutrition/cooking knowledge and skills, the VV program will help participants increase their F&V consumption.

2.0 Scientific Endpoints

2.1 Describe the scientific endpoint(s), the main result or occurrence under study.

NOTE: Scientific endpoints are outcomes defined before the study begins to determine whether the objectives of the study have been met and to draw conclusions from the data. Include primary and secondary endpoints. Some example endpoints are: reduction of symptoms, improvement in quality of life, or survival. Your response should **not** be a date.

Response:

Determine the impact of a mobile market (MM), the Veggie Van (VV), on lower-income (LI) communities using a randomized controlled study design and intent-to-treat analysis, by measuring:

- a) Reported consumption of F&V at baseline, and 12 months
- b) Body Mass Index (BMI) at baseline and 12 months
- c) Dermal Carotenoids using a finger scan technology called the “Veggie Meter” at baseline and 12 months
- d) Psychosocial measures (self-efficacy, perceptions of access to fruits and vegetables, shopping behavior and attitudes) at baseline and 12 months

3.0 Background

3.1 Provide the scientific or scholarly background, rationale, and significance of the research based on the existing literature and how it will contribute to existing knowledge. Describe any gaps in current knowledge. Include relevant preliminary findings or prior research by the investigator.

Response: Consumption of F&V is an important dietary component of disease prevention. Adults who consume fewer foods high in saturated fat, sodium, and sugar in favor of fresh F&V are less likely to develop heart disease, diabetes, certain types of cancer, and are more likely to sustain a healthy weight (1). However, in the United States, substantial socioeconomic disparities exist in the prevalence of chronic disease, and lower rates of healthy behaviors among LI Americans are significant contributors (2, 3). Some studies indicate that limited access to fresh F&V and healthy foods coupled with a higher prevalence of fast food outlets in LI neighborhoods are partially responsible for poor diets among residents (4); however, the research is mixed. Randomized controlled trials evaluating changes in the food environment are needed to better understand the relationship between food access and diet. An intervention study conducted in North Carolina at 12 community sites reported that those that regularly frequented a Veggie Van over 6 months increased their intake of fruit and vegetables by 1 cup greater than those who did not utilize the Veggie Van. This study will assess the effectiveness and sustainability of a MM program, Veggie Van, to coordinate, distribute, and sell affordable F&V in LI communities and food deserts in the Northeast, Midwest, and Southeastern regions of the United States. It will contribute to the literature describing the impact of the food environment on individual dietary behaviors. In addition, we will assess implementation measures to determine standards for successful and sustainable MMs. This data will be used to refine a VV toolkit for future MM efforts.

We will test the effectiveness of the VV model across multiple organizations and sites to understand what factors are associated with dietary change and sustainability.

3.2 Include complete citations or references.

Response:

4.0 Study Design

4.1 *Describe and explain the study design (e.g. case-control, cross-sectional, ethnographic, experimental, interventional, longitudinal, observational).*

Response: This Veggie Van effectiveness and implementation study, funded by the NIH, will be overseen by Drs. [name], [name], Co-Investigator, [name], Co-Investigator, and [name], Co-Investigator. This study will be coordinated by project coordinators and staff at UB and UNC.

For Aim 2 of the study, all study related procedures will be carried out by UB staff.

Aim 2: After 9 qualified organizations* have been identified among applicants, we will randomize proposed MM sites (33 total across all partner organizations), to an intervention (MM program implementation) or comparison condition (extended planning). Randomization will be stratified within each organization so that each organization will have 2 intervention and 2 comparison sites. One organization will have 5 sites. The 5th site will allow for more thorough testing of protocol procedures. This ensures that study groups will be balanced at the organizational level. The condition for which each proposed MM location was selected will be communicated at the time of award. Organizations will communicate to intervention sites that they want to open a MM at that location within the next year. Organizations will communicate to comparison sites that they want to work with them on a food systems planning process to determine if a MM program is the right fit for their location. At the end of the year-long planning process with comparison sites, the organization and proposed MM site will decide together how to proceed (start a MM, apply for grant funding for a different project; etc.).

Both arms will undergo community engagement efforts that serve to both identify potential research participants and engage them in the planning for a MM. Intervention sites will work with a community advisory committee to develop an engagement plan to raise community awareness of the forthcoming MM. Comparison sites will work with a community advisory committee to engage community members in a food access planning process.

Both intervention and comparison sites will distribute sign-up forms as part of the community engagement process. UB staff will identify from the sign-up forms those interested in participating in the study. Consent will be obtained via phone. Phone surveys and in-person data collection will then be completed.

- Baseline and 12 month Follow-Up Survey will include dietary-related psychosocial measures (self-efficacy to purchase, prepare, and eat fresh F&V), shopping behavior and attitudes, process measures, and demographics. At follow-up they will also answer qualitative questions related to program implementation. These surveys will be administered over the phone and collected using REDCAP. Questions assessing changes in food behavior due to COVID will also be assessed at baseline and follow-up.
- Our main individual-level outcome, change in F&V intake at 12 months, will be measured through four 24-hour recalls (2 at baseline and 2 at 12 months) which will be administered over the phone by trained interviewers. One recall at each time point will be from a weekday and the other from a weekend day. Recalls will be collected using the Nutrition Data Systems for Research (NDSR) computer-based software application. A participant will receive The Food Amounts Booklet via mail after the baseline survey to have as a visual reference for the 24-hour recalls.
- In addition to survey data, body mass index (BMI) and dermal carotenoids will be measured at in-person data collection events at baseline and 12 months.
 - Dermal carotenoids will be measured using a finger scan technology called the “Veggie Meter” which is thought to be a valid indicator of dietary carotenoid consumption.
 - BMI will be calculated from height and weight.

We are aware that there is the potential that a comparison participant may be exposed to the intervention. In previous work, this only occurred in 1 out of nearly 100 control participants.

**(update 1-7-2020: The 9 organizations that have been selected include: 1. Massachusetts Avenue Project (Buffalo, NY), 2. Urban Fruits and Veggies (Buffalo, NY), 3. Local Matters (Columbus, OH), 4. The Bulb (Charlotte, NC; 5. Mobile Oasis (Greensboro, NC); 6. Nuestras Raices (Holyoke, MA); 7. Family Residences and Essential Enterprises, Inc. (Long Island, NY); 8. Community Food Initiatives (Athens, OH); 9. Feast Down East (Wilmington, NC).*

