11.0 Study Timelines

11.1 Describe the anticipated duration needed to enroll all study subjects.

Response: Through community engagement efforts, we anticipate being able to recruit the majority of needed participants during the 2-month community engagement phase for each site. Recruitment will span a total of two years to enroll all 990 subjects at the 33 sites. In the event that we are not able to reach 30 participants at a given site, an additional month will allow partner organizations to continue recruitment efforts.

11.2 Describe the duration of an individual subject's participation in the study. Include length of study visits, and overall study follow-up time.

Response: The study will span over 12 months and will include 2 data collection time-points: baseline and at 12 months. Participants will be contacted approximately 8 times (4 times at baseline, 4 times at 12 months) to complete:

1. Screening/verbal consent (20 Minutes) & Baseline Survey (25 Minutes) (some participants may want to do survey during a separate call)
2. Baseline 24-hour recall call (30 Minutes)
3. Baseline 24-hour recall call (30 Minutes)
4. Baseline in-person data collection height/weight, dermal carotenoids (15 Minutes)
5. Follow-up Survey (25 Minutes)
6. Follow-up 24-hour recall call (30 Minutes)
7. Follow-up 24-hour recall call (30 Minutes)
8. Follow-Up in-person data collection height/weight, dermal carotenoids (15 Minutes)

Total participation for the study is expected to be approximately 4 hours. Phase 2 participants will complete 24-hour recalls during 12-month follow up only. Phase 2 participants that are currently enrolled in the study will be reconsented at follow-up to inform them that they are eligible to complete follow-up diet recalls and can earn an additional incentive for completing.

Sub-study: Baseline: Same survey as described above. In addition, a semi-structured interview will last 30-40 minutes and will take place within 2 months of the baseline survey. The follow-up survey will take place at 12-month follow-up as described above.

11.3 Describe the estimated duration for the investigators to complete this study (i.e. all data is collected and all analyses have been completed).

Response: The expected study duration is 5 years.

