Partner organizations will choose two sites they would start working with first based on timeline and readiness. These two sites will be paired for the purposes of randomization; one will be randomized to the mobile market site (intervention) and the other to the planning site (control). The same process will be used for the remaining pairs of sites as applicable. Partner organizations will run a mobile market following the Veggie Van model for at least one year at community sites randomized to the mobile market intervention. Planning sites partake in a year-long food access planning process to help determine if the surrounding community would benefit from a mobile market at that location. After one year, the partner and the planning site can decide to implement a mobile market, or another food access program based on community feedback gathered through the planning activities. Two months prior to the launch date of both the mobile market site and the planning site activities, partner organizations work jointly with community sites to engage the community to raise awareness of the mobile market and to recruit potential customers to participate in the Veggie Van Study.

Partner organizations will identify individuals who are interested in learning more about a mobile market in their community. To facilitate recruitment to the Veggie Van study, the partner and community site will utilize interest forms or sign-up sheets to collect community member contact information. If community members indicate interest in participating in the Veggie Van Study, the research team will contact them to screen, provide consent, and enroll into the study.

[figure not shown]
The goal is to recruit at least 30 participants at each of 32 proposed mobile market sites (960 total). Eligible individuals include those at least 18 years old, ability to speak English and/or Spanish, are the primary grocery shopper for their household, and live near or otherwise regularly frequent the community site. A threshold was established to ensure that market sites will be serving a predominantly lower-income community and that the study team is sampling from the appropriate target population. At least 60% of eligible sign-up forms are required to be from individuals that self-identify as receiving government assistance such as: the Supplemental Nutrition Assistance Program (SNAP), the Special Supplemental Nutrition Program for Women,

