(race $p=.01$; income: $p=0.02$). Including the baseline values as a covariate in an analysis of covariance (ANCOVA) is known to be a more powerful test than a group comparison of baseline to post-intervention change (42, 43). ANCOVA is not distorted by regression towards the mean bias, whereas a change analysis is subject to that bias (42, 43). We also conducted a sensitivity analysis excluding extreme F&V reporters, defined as participants who had a change (increase or decrease) greater than 10 servings of F&V per day based on generating histograms and identifying outliers in the data distribution. We conducted additional analyses comparing change in F&V intake for those who reported ever purchasing from VV (VV users) to those who did not report shopping at VV (VV non-users), including delayed-intervention control participants. Due to major disruptions to VV operations in the beginning of the study period (2020), we also looked for differences among a sub-sample of sites that launched after the peak of COVID-19 related closures defined as launching in 2021 or later (i.e., post-covid sites). All secondary outcome analyses were conducted using GLMMs and controlled for baseline covariates of interest and clustering within sites.

Additional analyses by question set can be found below:

Question Set	Answer options	Variable Creation	Analysis Plan
Demographics (13) Weight is asked again at follow-up	various	Will combine categories with small numbers of respondents BMI: created from height and weight	
For all main outcomes we need to control for site and relevant demographic variables
 
 1. Descriptive 2. Will test for differences between Ix and Control groups and include any variables that differ as co-variates in outcome analyses 3. BMI is Aim 1 outcome- compare intervention and control at 6 and 12 months. We expect BMI to stay the same for intervention at 6 months and decrease at 12 months whereas control will increase over time.

NCI F&V Screener (11)*	Frequency (per day, week or month) plus Portion Size	See below for scoring	Aim 1 Outcome. We hypothesize an increase in F&V consumption for intervention compared to control at 6 months.

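### Protocol and SAP describe different site allocation procedures; only the SAP's pair rule balances arm over launch wave, and the primary models include neither stratum nor launch period

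*Protocol*

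**What the plan says.** **Protocol 4.1** sets the allocation at organisation level: "Randomization will be stratified within each organization so that each organization will have 2 intervention and 2 comparison sites". One organisation has a fifth site. No pairing is mentioned. On disclosure it says: "The condition for which each proposed MM location was selected will be communicated at the time of award". On timing it says only: "Organizations will communicate to intervention sites that they want to open a MM at that location within the next year". It does not say who sets the order in which sites start.

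**SAP section 2** begins after the partner organisations have been selected: "Partner organizations will choose two sites they would start working with first based on timeline and readiness". Those two sites form a pair, with one drawn to the market arm and the other to planning. Then: "The same process will be used for the remaining pairs of sites as applicable". The SAP gives no date for each pair's draw or for the disclosure of its result.

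**On timing**, Protocol 11.1 says: "Recruitment will span a total of two years to enroll all 990 subjects at the 33 sites". SAP section 6 reports major disruption of market operations in 2020 and examines a subgroup of sites that launched in 2021 or later.

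**On analysis**, the primary models in Protocol 17.1 and SAP section 6 use a random intercept for site. Neither states a term for pair, organisation or launch period. Protocol 17.1 names organisation only as a possible moderator in exploratory interaction models.

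**The concern.** Launch date is a plausible prognostic factor here. A market that opened in 2020 may have delivered less of the intervention than one that opened later, and diet and shopping may also have differed between those periods. An allocation rule that balances arm over launch wave removes that difference by design, while one that does not leaves it to chance or to whoever sets the dates.

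Two things depend on which rule was used. The first is the stratum that the primary analysis should carry, which is the pair or the organisation. The second is the status of the 2021-or-later subgroup. If pairs were fixed, drawn and launched together, that subgroup consists of intact randomised pairs. If arms were disclosed first and launch dates set afterwards, it is selected on something that happened after randomisation. The documents do not let a reader tell which applies.

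**Working it through.** The plan gives no figure on this point, so there is none to reproduce.

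**1. Possible allocations in a four-site organisation.** Call the first two sites to start A and B, and the later two C and D.
- Unpaired 2:2 (Protocol 4.1): C(4,2) = 6 allocations. In 2 of them (A and B both market, or both planning) the first wave is all one arm. Probability 2/6 = 1/3.
- 1:1 within pairs A–B and C–D (SAP section 2): 2 × 2 = 4 allocations, none with a one-arm wave.

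**2. Number of organisations.** SAP 2.1 plans 8 organisations and 32 sites, four each. Nine organisations with four sites, one of them with five, would need 8 × 4 + 5 = 37 sites, not the 33 in Protocol 4.1. Eight is therefore the usable number.
- Expected number with a one-arm first wave under the unpaired rule: 8 × 1/3 = 2.7.
- Probability of at least one: 1 − (2/3)^8 = 0.96.

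**3. Chance imbalance over the trial, with launch order unrelated to arm.** With 16 sites per arm, each one-arm first wave moves the between-arm difference in early-launch share by 2/16 = 1/8, up or down with probability 1/6 each.
- Mean difference: 0.
- SD: sqrt(8 × 1/3)/8 = 0.20.
- Probability of a difference of 25 points or more in either direction: 0.35.
- Under the pair rule with joint launch, the difference is 0.

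**4. What a systematic order could do (assumed inputs only).** Bias = period effect on change in intake × between-arm difference in early-launch share. Neither input is in the documents. Suppose that a net 4 of 8 organisations launched both market sites first (share difference 4/8 = 0.5), and take period effects of 0.25, 0.5 and 1.0 cup/day. For scale, use the SAP 2.1 inputs (SD 2.7, ICC 0.08, 21 per site) with 16 sites per arm:
- Design effect: 1 + 20 × 0.08 = 2.6.
- SE: 2.7 × sqrt(2/(16 × 21/2.6)) = 0.336.

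| Assumed period effect (cup/day) | Bias (cup/day) | One-sided type I error if bias favours the market (nominal 5%) | Power at 1 cup/day if bias goes against it (nominal 91%) |
|---|---|---|---|
| 0.25 | 0.125 | 10% | 83% |
| 0.5 | 0.25 | 18% | 72% |
| 1.0 | 0.5 | 44% | 44% |

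The table shows sensitivity. It is not an estimate of what happened.

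**The case against.** The strongest reply is that the two texts describe one procedure at different levels of detail. Two 1:1 pairs give exactly 2 market and 2 planning sites, so SAP section 2 could be the method behind the protocol's summary. If every pair had been fixed and drawn before award, telling the organisation all arms at award would do no harm. The 2:2 total is indeed compatible with pairing. The rest of the reconciliation is strained, because the SAP places the choice of sites after the organisations had become partners, and neither document says that all pairs were drawn before award.

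A reader might infer something stronger: that under the protocol organisations chose their launch order knowing the arms, so that arm is confounded with launch period. The documents do not support that. The protocol is silent on who sets the order. The only text that gives organisations such a choice is in the SAP, and there the choice comes before that pair's draw. Nor should the 1/3 be read as bias. It has mean zero, and any randomisation not stratified on time carries such imbalance.

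Three further points are fair:
- The SAP refers to the launch of the market site and of the planning activities together, which suggests a joint start, although it does not state a common date for each pair.
- The 2021-or-later analysis is a response to the disrupted period. It does not by itself secure balance between arms.
- The SAP is dated 2/3/2025 and reports analyses in the past tense, so changes to the draw are probably too late. Documentation and the model can still be corrected.

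**Conclusion.** The concern holds as an unresolved difference between two current texts that affects the analysis. The procedures differ (6 against 4 possible allocations per four-site organisation), and only the pair rule guarantees one site per arm in each launch wave, on the condition that paired sites launch together. If the unpaired rule was used, about 2.7 of 8 organisations would be expected to start with both sites in one arm by chance alone. This assumes four-site organisations with two starting waves of two sites each.

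Systematic confounding of arm with launch period is possible only if the launch order was set after the arms were disclosed. The documents neither show nor exclude that, and they give no basis for sizing it. The point is worth acting on because the information needed should already exist, the correction costs little, and the primary models have no term that would absorb the problem.

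**What to change.** 1. **Reconcile Protocol 4.1 and SAP section 2** to the rule actually used, by organisation if it varied. The 2:2 total can stay. If arms really were communicated at award, keep that statement as a record of what was done. For any draw not yet made, use the pair rule and disclose one pair at a time. State how the fifth site, which has no partner, was allocated.
2. **Give the dates** of pair formation, draw, disclosure and launch for each organisation, and tabulate launch date by arm.
3. **Put the stratum actually randomised in the primary model:** pair where pairs were fixed before the draw, organisation otherwise.
4. **Add launch period** (2020 against 2021 or later) as a sensitivity adjustment.
5. **If launch dates were set after disclosure,** label the 2021-or-later subgroup as selected after randomisation.

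**Cost:** a site-level log, some wording, and degrees of freedom. With 32 sites, fixed terms for 8 organisations reduce the between-site degrees of freedom from 32 − 2 = 30 to 32 − 8 − 1 = 23. Fixed terms for 16 pairs reduce them to 16 − 1 = 15. Because the SAP's analyses appear to have been run, the model with the stratum should be reported beside the site-only model and dated as a later addition.
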